6.4 Product formulation

The eluted plasmid preparations will be resuspended in sterile, preservative free-PBS. A small sample (100 µL) will be removed aseptically and the concentration tested using a certified NanoDrop spectrophotometer, Qubit Fluorometer or similar device. Typically, the eluted DNA is in the range of 3-4 mg/mL. The DNA product will be diluted to 2 mg/mL using sterile, preservative-free PBS, and aseptically added to 2.0 mL cryovials from Nalgene (Catalog# 5000-0020, Lot# 616412). The vials are made of polypropylene with a high-density polyethylene closure. They are externally-threaded for aseptic technique. They have a sealing ring in conjunction with specially designed threads. A white marking area, fill line, and graduations are printed on the vials with white paint. They are radiation-sterilized, non-cytotoxic, non-pyrogenic, and are RNase/DNase-free.

We plan to synthesize enough DNA for approximately 20 vials. We anticipate that 12 vials will be required for vaccination (2 vials per time point times 6 time points), and 5 vials will be required for product release tests. We are targeting 20 vials to have a reserve stock.

Following vialing, we anticipate that 4 vials (#1, 4, 10, 19) will be used for product release testing. Vials 1 and 19 will be used to test sterility and represent the beginning and end of the vialing procedure. Two additional vials will be used for the other product release tests listed in Table 3.

If any contamination would be detected in our plasmid samples, we would initiate an alcohol precipitation step. This procedure is basically the final stage of the gigaprep purification, where the soluble DNA is

precipitated using 2x volumes of cold isopropanol and the DNA is pelleted by centrifugation. The pellet is washed in 70% ethanol and air dried. This procedure is a standard method for eliminating any microbiologic contamination in DNA.

6.5 Product release tests

A key issue in the quality control of plasmid DNA for human use is the development of analytical methodologies capable of fully characterizing the product in its final form, ensuring the production of a consistent product. The following list of release criteria, analytical methodologies, and specifications has been adapted from [73]. Neoantigen DNA vaccines will be tested for the following specifications.

TABLE 3: Neoantigen DNA vaccine product release tests			
Criteria	Method	Specification	Test Site
Plasmid activity	Transfect cells, RT-PCR	Polyepitope mRNA present	[name] Laboratory
Residual kanamycin	USP 29 <81>	< 8 mcg/mL	Alcami or equivalent
Plasmid homogeneity	Agarose gel electrophoresis	≥80% closed circular	[name] Laboratory
Residual RNA	Agarose gel electrophoresis	Less than 1%	[name] Laboratory
Residual bacterial chromosomal DNA	Agarose gel electrophoresis	Less than 1%	[name] Laboratory
Plasmid identity	Restriction analysis	As expected, no extraneous bands	[name] Laboratory
Appearance	Visual	Clear and colorless, free of particulates	[name] Laboratory
pH	Calibrated pH meter	Report pH	Biologic Therapy Core Facility
DNA concentration	Nano-drop spectrophotometer	Greater than 1 mg/mL	[name] Laboratory
Residual proteins	BCA reagent colorimetric	Less than 1% (< 21 µg/mL)	[name] Laboratory, Biologic Therapy Core Facility, or equivalent
Residual isopropanol, EtOH	USP <467>	Less than 5000 ppm	PACE Analytics or equivalent
Endotoxin	Chromogenic Limulus amoebocyte lysate assay	Less than 175 EU/mL	Biologic Therapy Core Facility
Sterility	USP <71>	No growth	Biologic Therapy Core Facility

Alternatively, we will perform studies to demonstrate that the manufacturing process removes residual kanamycin, RNA, bacterial chromosomal DNA, proteins, isopropanol and EtOH below the specification levels, and not perform these residual studies on each lot. To date, testing on each lot has shown that residual kanamycin is undetectable and residual isopropanol and EtOH is consistently below the specification. This testing will no longer be performed. The criteria for sterility meets specification if no growth after 7 days. The sterility culture will be held and monitor for 14 days as per USP <71>.

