4.6 Randomization

Twenty-four patients will be enrolled. Patients will be randomized for participation in a 1:1 ratio to receive either neoantigen DNA vaccine alone or neoantigen DNA vaccine plus durvalumab. The randomization table will be generated using the SAS program PROC PLAN. Randomization will take place after the manufacture of the vaccine and after eligibility has been reconfirmed.

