6 INVESTIGATIONAL AGENT: NEOANTIGEN DNA VACCINES

6.1 Chemical name and structure

The neoantigen DNA vaccines are also known as DNA plasmid vector expressing tumor-specific antigens.

Neoantigen DNA vaccines will be designed in the [name] laboratory and manufactured at the Siteman Cancer Center Biological Therapy Core Facility based on the following general steps:

- (1) Breast cancer tissue and normal lymphocytes will be obtained from breast cancer patients who are eligible for the phase 1 clinical trial.
- (2) Tumor/normal exome sequencing and tumor cDNA-capture sequencing will be performed to identify candidate neoantigens.
- (3) Candidate neoantigens will be prioritized based on epitope prediction algorithms and *in vitro* studies.
- (4) Personalized polyepitope inserts integrating the prioritized neoantigens will be designed in the [name] laboratory and then synthesized and cloned into the pING parent vector by Blue Heron Biotech.
- (5) Master cell banks will be established and validated at WUSM.
- (6) The neoantigen DNA vaccines will be manufactured and vialled at WUSM.
- (7) The neoantigen DNA vaccines will undergo product release tests at WUSM and other sites prior to investigational use.

The neoantigen DNA vaccines will be manufactured in the SCC Biologic Therapy Core facility. Standard Operating Procedures for the GMP manufacture of the neoantigen vaccines have been established and are in accordance with "CGMP for Phase 1 Investigational Drugs 2008," and "Considerations for Plasmid DNA Vaccines for Infectious Disease Indications 2007."

Each neoantigen DNA vaccine drug product is composed of a deoxyribonucleic acid (DNA) plasmid purified from *E. Coli*. The pING parent vector was obtained from [name]. at Memorial Sloan Kettering Cancer Center (Figure 2). The pING vector has been used extensively in preclinical DNA vaccine studies [71, 72], and in human clinical trials, including a clinical trial at WUSM (ClinicalTrials.gov identifier: NCT00807781). The mammaglobin-A DNA vaccine is based on the pING vector and was manufactured at WUSM in the SCC Biologic Therapy Core Facility using manufacturing processes almost identical to the ones outlined here).

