6.6 Stability

The neoantigen DNA vaccines will be stored in the Biologic Therapy Core Facility in a -80°C freezer. The freezer used for storage is monitored 24/7 by Johnson Controls monitoring system with dedicated on-call personnel to address any aberrant occurrences. In addition, daily manual monitoring is applied. Overall, we anticipate no problems with plasmid stability as stability is considered to be one of the advantages of the DNA vaccine platform, and plasmid DNA formulated in PBS is considered to be very stable.

We are currently storing similar investigational DNA vaccines in the Biologic Therapy Core Facility in a -80°C freezer. These investigational DNA vaccines were manufactured in the Biologic Therapy Core Facility using an almost identical manufacturing process as the one proposed here, are based on the pING parental vector and are thus very similar in size and composition, and are formulated similarly in PBS at 2 mg/mL. These DNA vaccines have remained stable over a 3- year period.

We do not anticipate that long-term stability testing will be required. As each lot of vaccine is personalized to a specific patient, we anticipate that the vaccine will be used within 6 months of completion of the product release tests.

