6.7 Labels

Each neoantigen DNA vaccine product will be made as a single lot ensuring that the labeled product is unique and consistent for this trial. Please see the sample label below. Prior to administration a time out will be performed to confirm subject identity, and the investigational agent to be administered. This will be performed by the clinical research associate, the oncology nurse trained to administer the vaccine by electroporation and the experimental pharmacist.

SCC Biologic Therapy Core Facility

Saint Louis, MO
Store at -80°C
WUSM PPDV #2

Subject Study #, Subject Initials

LOT #	1
Vial #	003
Concentration	2mg/mL
Volume	1.2mL
Date	mm/dd/yyyy

CAUTION Investigational drug limited by federal law to investigational use

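### Section 6.5 counts a vaccine lot as sterile at day 7 of a culture read to day 14, and no later step requires the final reading before the first injections

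*Combined protocol and SAP*

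**What the plan says.** Table 3 in section 6.5 lists sterility by USP <71> with a no-growth specification and gives no day. The text under the table supplies two: "The criteria for sterility meets specification if no growth after 7 days", followed by "The sterility culture will be held and monitor for 14 days as per USP <71>". No reason is given for the earlier point.

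Section 6.1 sets the general rule: "The neoantigen DNA vaccines will undergo product release tests at WUSM and other sites prior to investigational use". Section 6.6 gives an outer limit on use: "we anticipate that the vaccine will be used within 6 months of completion of the product release tests".

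The steps between manufacture and dosing are in other sections. Section 4.6 says: "Randomization will take place after the manufacture of the vaccine and after eligibility has been reconfirmed". Section 8.1 places Day 1 after the end of standard therapy. Section 6.7 describes the last check: "Prior to administration a time out will be performed to confirm subject identity, and the investigational agent to be administered".

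For a lot that fails, section 6.4 offers one action: "If any contamination would be detected in our plasmid samples, we would initiate an alcohol precipitation step". It then asserts: "This procedure is a standard method for eliminating any microbiologic contamination in DNA". It mentions neither re-vialing nor repeat testing.

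**The concern.** A sterility specification protects the patient only if the result that satisfies it is known before injection. Here the protocol names a method, says that the method runs 14 days, and treats the result as satisfactory halfway through. If Day 1 falls between the two readings, the patient receives an intramuscular product on an interim result.

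The stakes are patient safety and the reading of the primary endpoint, which is safety. Section 9.1.2 lists injection-site infection as a risk, and its reassurance about infection rests on skin preparation and sterile equipment, which presupposes a sterile product. An infection or fever caused by the lot could be attributed to the vaccine. Under section 14.1, one related serious event halts injections and enrollment, as does the same Grade 2 or higher event, such as fever, in two subjects when it is judged probably or definitely related. With a separate lot for each patient, a manufacturing fault in one lot would be hard to tell from toxicity of the vaccine strategy.

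The reprocessing route raises a related but smaller question. A precipitated and refilled lot is physically a different fill from the one sampled, and section 6.4 does not say that it is tested again.

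**Working it through.** The plan states no figure to reproduce on this point. The check is mainly a comparison of sections, with two small pieces of arithmetic.

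**1. Unread part of the test.** Inputs: pass point 7 days and culture length 14 days, both from section 6.5. 14 − 7 = 7 days, half of the culture.

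**2. Does a later step require the final reading?**

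- Section 6.1: release tests precede use. At day 7 the sterility criterion as worded is already met, so this rule does not force a wait.
- Section 4.6: randomization follows manufacture and the eligibility re-check. Sterility status is not mentioned.
- Section 8.1: Day 1 is tied to completion of standard therapy, not to the culture.
- Section 6.7: the time-out confirms the subject and the agent, not the status of the lot.
- Section 6.6: the 6 months run from completion of release testing. This is a maximum, with no minimum interval.

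None of the five closes the gap.

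**3. Which doses are exposed?** Section 8.1 requires at least 21 days between injection days. If the first injection were given as soon as the day-7 reading passed, the second time point would fall no earlier than culture day 7 + 21 = 28, which is after day 14. Only time point 1, with its two injections, can precede the final reading.

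**4. How often?** The interval from vialing to Day 1 is not given, so the share of lots dosed between the two readings cannot be calculated. It may be zero.

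**5. What would waiting cost?** At most 7 days. The Study Plan puts standard therapy at about 6 months. Section 6.6 anticipates use within 6 months of release testing, with storage at −80°C, and reports similar vaccines stable over 3 years. Stability gives no visible reason to hurry.

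**6. Does the vial plan allow a retest after reprocessing?** Inputs from section 6.4: about 20 vials; 2 per time point × 6 time points = 12 for dosing, which agrees with the plan's own 12; and either 5 or 4 for release tests, since the section gives both numbers.

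| Test vials | Reserve | After a second full set of tests |
|---|---|---|
| 4 | 20 − 12 − 4 = 4 | 4 − 4 = 0 |
| 5 | 20 − 12 − 5 = 3 | 3 − 5 = −2 |

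These counts ignore material lost in precipitation. Vials 1 and 19 were chosen to represent the beginning and end of the original fill, so their results cannot stand for a refilled lot.

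**The case against.** The strongest reply is that the two sentences describe a deliberate two-stage procedure and do not contradict each other. Whether release at day 7 is acceptable may be settled in the IND file or in the manufacturing procedures that section 6.1 says are established. Figure 4, the schematic of manufacture and release testing, is not shown in the text available for review. This stands as a caution: the point may already be covered elsewhere, and then a cross-reference would do. It does not remove the problem in the protocol as written, which gives no reason for the early pass point.

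A reader might infer that the plan is silent on late growth. It is not. The contamination clause in section 6.4 has no time limit, so by its wording it covers growth on days 8 to 14. It cannot help with doses already given. General routes also exist: reporting of unanticipated problems (sections 13.1.2 and 20.5), the investigator's power to halt (section 14.1), and adverse-event follow-up 24 to 48 hours after each vaccination (section 10). The lack of a lot-specific notification procedure is missing detail that may sit in release procedures.

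A reader might also infer that a reprocessed lot goes out untested. Section 6.1 can be read to require release tests on any product before use, and section 9.1.2 says that every lot is tested for endotoxin. The fair criticism is that section 6.4 does not make this explicit.

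The clinical risk should not be inflated. Section 3.1 excludes recent chemotherapy (within 30 days) and active infection, and requires adequate neutrophil counts.

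**Conclusion.** The concern holds in a limited form. The sterility criterion is met with 7 of 14 culture days unread, and no step in the protocol requires the remaining reading before Day 1. The documents therefore do not exclude giving the two injections of time point 1 on an incomplete test. All later time points fall after the final reading.

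The documents do not support the stronger statement that non-sterile vaccine will be given. No passage schedules an injection before culture day 14, and after about 6 months of standard therapy the final result may often be in hand. This makes it cheap to require the final reading.

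The conclusion assumes that nothing outside the protocol, such as Figure 4 or the manufacturing procedures, already ties first use to the final reading. The reprocessing point is secondary: a clarification of section 6.4, with a practical limit set by the reserve of 3 or 4 vials.

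**What to change.** In section 6.5, reconcile the two sentences so that the final 14-day no-growth reading governs release for first use, and describe day 7 as an interim reading for planning. Growth on days 8 to 14 would then be found before any patient is dosed, and a separate procedure for patients already injected would not be needed. If the release procedures already require this, cite them.

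In section 6.4, state that a lot reprocessed after contamination is treated as a new lot and repeats the release tests still in force, including sterility and endotoxin. This need not mean every row of Table 3, because section 6.5 has discontinued residual kanamycin, isopropanol and ethanol testing. In the same edit, settle whether 4 or 5 vials go to release testing, and say what happens if too few remain for retesting and dosing.

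The cost is protocol wording and up to 7 days' delay to Day 1 when a lot finishes late. Ordinary lots need no new test. A reprocessed lot may need a larger fill or a fresh production run.

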6.6 Stability

The neoantigen DNA vaccines will be stored in the Biologic Therapy Core Facility in a -80°C freezer. The freezer used for storage is monitored 24/7 by Johnson Controls monitoring system with dedicated on-call personnel to address any aberrant occurrences. In addition, daily manual monitoring is applied. Overall, we anticipate no problems with plasmid stability as stability is considered to be one of the advantages of the DNA vaccine platform, and plasmid DNA formulated in PBS is considered to be very stable.

We are currently storing similar investigational DNA vaccines in the Biologic Therapy Core Facility in a -80°C freezer. These investigational DNA vaccines were manufactured in the Biologic Therapy Core Facility using an almost identical manufacturing process as the one proposed here, are based on the pING parental vector and are thus very similar in size and composition, and are formulated similarly in PBS at 2 mg/mL. These DNA vaccines have remained stable over a 3- year period.

We do not anticipate that long-term stability testing will be required. As each lot of vaccine is personalized to a specific patient, we anticipate that the vaccine will be used within 6 months of completion of the product release tests.

6.7 Labels

Each neoantigen DNA vaccine product will be made as a single lot ensuring that the labeled product is unique and consistent for this trial. Please see the sample label below. Prior to administration a time out will be performed to confirm subject identity, and the investigational agent to be administered. This will be performed by the clinical research associate, the oncology nurse trained to administer the vaccine by electroporation and the experimental pharmacist.

SCC Biologic Therapy Core Facility

Saint Louis, MO
Store at -80°C
WUSM PPDV #2

Subject Study #, Subject Initials

LOT #	1
Vial #	003
Concentration	2mg/mL
Volume	1.2mL
Date	mm/dd/yyyy

CAUTION Investigational drug limited by federal law to investigational use

6.8 Siteman Cancer Center Investigational Pharmacy

The Investigational Pharmacy is located on the 7th floor of the Center for Advanced Medicine within the chemotherapy administration area of the Siteman Cancer Center. The pharmacy is locked and secured with entry only via an authorized swipe card entry system. Three pharmacists, including a pharmacist with responsibility for investigational agents, and two technicians are employed full-time. Two freezers (-70°C and -20°C) and one refrigerator have been designated for studies. Room temperature shelving extends over 300 feet. There are three IV admixture hoods. Two vertical flow hoods are used for preparation of chemotherapy agents and a laminar flow hood is used for non-chemotherapy agents. There were a total of 13,260 chemotherapy prescriptions filled in 2004. Pharmacy hours of operation are Monday through Friday from 7:00 am to 5:30 pm. The investigational pharmacist will obtain the vaccine from the TBC Facility and dispense the vaccine to the nurse who will be administering the agent to the patient.

6.9 Investigational agent administration

Each DNA vaccination will be 1 mL vaccine administered intramuscularly using an integrated electroporation administration system (TDS-IM system, Ichor Medical Systems). At each vaccination time point, patients will receive two injections at separate sites.

6.9.1 Introduction to electroporation

Electroporation (EP) is a potent delivery technique based on the *in vivo* application of electrical fields that may improve immune responses following the administration of plasmid DNA vaccines. The EP effect is induced through the propagation of electrical fields of sufficient magnitude and duration within a target region of tissue. These electrical fields produce a transient increase in the membrane permeability of cells exposed to the electrical field, allowing enhanced intracellular uptake of agents distributed within the interstitium of the local tissue. Of note, agent delivery occurs only where the agent of interest is present contemporaneously with the propagation of threshold level electrical fields. Numerous non-clinical studies have demonstrated that the application of EP can enhance gene expression and immune responses following plasmid DNA vaccine delivery.

Although DNA vaccines encoding antigens from a variety of cancers and infectious pathogens have exhibited considerable promise in non-clinical studies, clinical experience to date suggests that current administration methods may have insufficient potency to achieve the desired immune responses in humans. Poor delivery efficiency and low levels of antigen expression have been implicated as factors contributing to the sub-optimal responses observed to date [74, 75].

Electroporation (EP) is a potent physical delivery technique based on the *in vivo* application of electrical fields. The propagation of electrical fields of a sufficient magnitude within a target tissue induces a transient increase in cell membrane permeability, resulting in a significant improvement of intracellular uptake of exogenous substances. Shortly after pulse delivery, the cell membrane function stabilizes and cells within the affected tissue resume normal function. EP has been shown in non-clinical studies to be a potent method for delivery of DNA vaccines [40, 76-78].

EP has several important advantages that make it an appealing method for delivery of DNA vaccines. First, EP can reliably enhance delivery and expression of DNA antigens by 2-3 orders of magnitude. This improvement in delivery has been shown to enhance both cellular and humoral immune responses. Second, EP is a non-viral delivery method. As such, it has a favorable safety profile and does not elicit unwanted immune responses against the vector. Thus, the technique is particularly appropriate for indications likely to require multiple vaccine administrations to achieve response (e.g. prime / boost). It is also advantageous because the absence of immunogenic viral antigens minimizes potentially deleterious antigen competition, thereby ensuring that the immune response is concentrated on the antigen of interest. Lastly, unlike other non-viral approaches, EP is capable of inducing consistent responses from subject to subject, even at relatively low DNA doses.

